[REDACTED]

[REDACTED]

[REDACTED]

Other investigational therapies must not be used while the patient is on the study.

7. Duration of Therapy

Subjects will be treated for a total of 6 cycles. For subjects who have stable disease or better, treatment may continue until one of the following criteria applies:

- e. Inter-current illness that prevents further administration of treatment,
 - f. Unacceptable adverse event(s),
 - g. Patient decides to withdraw from the study, or
 - h. General or specific changes in the patient's condition render the patient unacceptable for further treatment in the judgment of the investigator.
- e. Evidence of disease progression by the IWG 2006 criteria, not applicable at bone marrow evaluation at day -10 of lead in phase.

Subjects who wish not to continue treatment will complete their end of study visit upon completion of cycle 6.

8. Duration of Follow-Up

Subjects will be followed as per calendar on treatment for 6 cycles. After 6 cycles, patients who continue on treatment will be followed monthly. Off treatment data on AML transformation and overall survival will be updated every 6 months or until death, whichever occurs first. Subjects removed from study for unacceptable adverse events will be followed until resolution or stabilization of the adverse event.

9. Criteria for Removal from Study

a. Subject Completion

A subject will be considered to have completed the study if the subject meets at least 1 of the following criteria:

- The subject has progressive disease.
- The subject died during the study.
- The subject experience a treatment related AE that led to withdrawal from the study.
- The subject starts new treatment for their underlying disease (MDS/CMML/AML).

b. Subject Withdrawal from Study

A subject may voluntarily withdraw from study medication or withdraw consent from the study at any time. The investigator may also, at his or her discretion, discontinue a subject from participating in the study at any time. The investigator and/or designated staff will record the date and the reason for subject withdrawal from the study.

c. Subject Withdrawal from Study Medication

If the subject is permanently withdrawn from treatment with study medication, but does not withdraw consent, the investigator must make every effort to have the subject complete all withdrawal assessments at the time of withdrawal, and complete all scheduled follow-up visits.

Treatment with study medication must be discontinued if:

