14. MEASUREMENT OF EFFECT

Definitions: Response and progression will be assessed according to modified International Working Group (IWG) 2006 criteria³⁴ (Appendix B).

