Stage 2: Enroll 21 more evaluable patients for a total of 45. If less than 14 of 45 patients achieve CR, then there is insufficient evidence to support continued study of this treatment. If at least 14 of 45 patients achieve CR, then there is sufficient evidence to support further study of APR-246 in combination with azacitidine in Phase 3. Up to 39 additional evaluable patients will be treated at the level of the MTD in the

Phase 2 portion of the trial.

This rule has the following operating characteristics: 90% power, with $\alpha=0.05$ under the null hypothesis that the proportion of patients achieving CR is $\leq 20\%$ versus the alternative hypothesis that it is $\geq 40\%$. This design has a probability of early termination equal to 0.66 if the true CR rate is 20%.

2. Statistical Analysis Methods

Demographic and clinical variables for the study patients will be summarized using descriptive statistics (mean, standard deviation, median, inter-quartile range, range, frequency counts and percentages). Safety and efficacy data will be analyzed overall as well as separately for each dose cohort when appropriate.

3. Safety Analysis

This analysis will include all subjects who have received any protocol treatment, regardless of patient eligibility. The number (%) of subjects with adverse events, serious adverse events, and adverse events leading to treatment discontinuation will be reported. Adverse events summary will be reported by type and severity. Laboratory parameters will also be summarized using descriptive statistics.

4. Efficacy Analysis: ITT

This analysis will include all subjects who have received any protocol treatment, regardless of patient eligibility or duration of treatment. Those who have no response assessment data due to reasons such as drop out of the study, withdrawal consent, or lost to follow-up will be treated as non-responders for various response evaluations. The proportion of subjects achieving the primary endpoint will be summarized. A 95% exact binomial confidence interval of the proportion will also be provided for all participants treated at the MTD. In addition, a second analysis of evaluable subjects will be performed. Evaluable subjects are defined as those who complete at least 3 cycles of therapy and complete the first on treatment bone marrow biopsy and aspirate to evaluate study drug response.

Analyses of the following secondary endpoints will be performed as well:

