- i. Duration of response defined as the time between achieving response and progression of disease.
- ii. OS at 8 months
- iii. Proportion of subjects achieving hematological improvement (HI), partial response (PR), complete response (CR), and/or marrow CR (mCR) by the IWG 2006 criteria (see appendix B)
- iv. Proportion of subjects who obtain a response as defined by IWG 2006 criteria with a baseline *TP53* VAF $\geq 20\%$ versus $< 20\%$ or high versus low nuclear p53 protein expression

- v. Correlation of *TP53* VAF with nuclear p53 protein expression as determined by IHC
- vi. Proportion of subjects who achieve $\geq 50\%$ reduction in *TP53* VAF.
- vii. Progression free survival (PFS) and OS in clonal responders ($\geq 50\%$ reduction in *TP53* VAF) versus non-responders
- viii. Profile expression of genes related to p53-mediated signal transduction before and after APR-246 treatment
- ix. Profile ROS production before and after APR-246 treatment
- x. AML transformation according to World Health Organization (WHO) criteria
- xi. OS
- xii. LFS
- xiii. Determine recurrent gene mutations in *ASXL1*, *BCOR*, *BRAF*, *CALR*, *CBL*, *CEBPA*, *CSF3R*, *DNMT3A*, *ETV6*, *EZH2*, *GATA2*, *GNAS*, *IDH1*, *IDH2*, *JAK2*, *KIT*, *KRAS*, *MPL*, *NF1*, *NPM1*, *NRAS*, *PDGFRA*, *PDGFRB*, *PHF6*, *PTPN11*, *RAD21*, *RUNX1*, *SETBP1*, *SF3B1*, *SMC1A*, *SMC3*, *SRSF2*, *STAG2*, *STAT3*, *STAT5b*, *TET2*, *TP53*, *U2AF1*, *WT1*, and *ZRSR2* at study entry and serially throughout treatment to assess changes in somatic mutation landscape.

Preliminary data on the above endpoints will prove to be very useful for further investigation of this protocol's treatment. Such data will be summarized appropriately in an exploratory fashion. Both point estimates and 95% confidence intervals will be reported, if feasible. Time-to-event endpoints such as OS and LFS will be summarized using the Kaplan-Meier product-limit method.

16. Laboratory Correlates

Unless otherwise specified, all laboratory correlates will be performed in the laboratory of [name] or at Genoptix medical laboratory.

1. Mutation analyses

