APPENDIX B

RESPONSE CRITERIA FOR SUBJECTS WITH MDS AND CMML ACCORDING IWG 2006 CRITERIA³⁴

ALTERING DISEASE NATURAL HISTORY	
Complete remission (CR)	Bone marrow: $\leq 5\%$ myeloblasts with normal maturation of all cell lines Persistent dysplasia will be noted Peripheral blood: Hemoglobin ≥ 11 g/dL Platelets $\geq 100 \times 10^9/L$ Neutrophils $\geq 1.0 \times 10^9/L$ Blasts 0%
Partial remission (PR)	All CR criteria if abnormal before treatment, except: Bone marrow blasts decreased by $\geq 50\%$ over pretreatment but still $> 5\%$ Cellularity and morphology not relevant
Marrow CR	Bone marrow: $\leq 5\%$ myeloblasts and decrease by $\geq 50\%$ over pretreatment Peripheral blood: if HI responses, they will be noted in addition to marrow CR
Stable disease (SD)	Failure to achieve at least PR, but no evidence of progression for > 8 weeks
Failure	Death during treatment Disease progression characterized by worsening of cytopenias, increase in % of bone marrow blasts, or progression to a more advanced MDS FAB subtype than pretreatment
Disease Progression (PD)	For subjects with: Less than 5% blasts: $\geq 50\%$ increase in blasts to $> 5\%$ blasts 5%-10% blasts: $\geq 50\%$ increase in blasts to $> 10\%$ blasts 10%-20% blasts: $\geq 50\%$ increase in blasts to $> 20\%$ blasts 20%-30% blasts: $\geq 50\%$ increase in blasts to $> 30\%$ blasts Any of the following: At least 50% decrement from maximum remission/response levels in granulocytes or platelets Reduction in hemoglobin (Hgb) concentration by ≥ 2 g/dL - Transfusion dependence
CYTOGENETIC RESPONSE	
Complete	Disappearance of the chromosomal abnormality without appearance of new ones
Partial	At least 50% reduction of the chromosomal abnormality
HEMATOLOGICAL IMPROVEMENT (HI)	
Erythroid response (HI-E) (Pretreatment < 11 g/dL)	Hgb increase by ≥ 1.5 g/dL Relevant reduction of units of RBC transfusions by an absolute number of at least 4 RBC transfusions/8 weeks compared with the pretreatment transfusion number in the previous 8 weeks. Only RBC transfusions given for a Hgb of ≤ 9.0 g/dL pretreatment will count in the RBC transfusion evaluation
Platelet response (HI-P) (Pretreatment $< 100 \times 10^9/L$)	Absolute increase of $\geq 30 \times 10^9/L$ for subjects starting with $> 20 \times 10^9/L$ Increase from $< 20 \times 10^9/L$ to $> 20 \times 10^9/L$ and by at least 100%
Neutrophil response (HI-N) (Pretreatment $< 1.0 \times 10^9/L$)	At least 100% increase and an absolute increase of $> 0.5 \times 10^9/L$

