PROGRESSION/RELAPSE CRITERIA FOR SUBJECTS WITH MDS/CMML

ALTERING DISEASE NATURAL HISTORY	
Disease Progression (PD)	
For subjects with:
 
Less than 5% blasts: $\geq 50\%$ increase in blasts to $> 5\%$ blasts
 
5%-10% blasts: $\geq 50\%$ increase in blasts to $> 10\%$ blasts
 
10%-20% blasts: $\geq 50\%$ increase in blasts to $> 20\%$ blasts
 
20%-30% blasts: $\geq 50\%$ increase in blasts to $> 30\%$ blasts
 
Any of the following:
 
At least 50% decrement from maximum remission/response levels in granulocytes or platelets
 
Reduction in hemoglobin (Hgb) concentration by ≥ 2 g/dL
 
Transfusion dependence

Disease transformation	Transformation to AML (30% or more blasts)
Relapse after CR or PR	
At least one of the following:
 
Return to pretreatment bone marrow blast %
 
Decrement of $\geq 50\%$ from maximum remission/response levels in granulocytes or platelets
 
- Reduction in Hgb concentration by ≥ 1.5 g/dL or transfusion dependence

HEMATOLOGICAL IMPROVEMENT	
Progression/relapse after HI	
At least one of the following:
 
At least 50% decrement from maximum response levels in granulocytes or platelets
 
Reduction in Hgb by ≥ 1.5 g/dL
 
- Transfusion dependence

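### Duration of response has no event for death without progression, WHO-based AML transformation keeps entrants who already have 20-30% blasts, and leukemia-free survival is undefined

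*Combined protocol and SAP*

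**What the plan says.** **Duration of response.** The synopsis, section 3.2.1 and section 15.4 share one definition: "Duration of response defined as the time between achieving response and progression of disease". None of them adds death or a censoring rule. Section 14 points to Appendix B for the criteria: "Response and progression will be assessed according to modified International Working Group (IWG) 2006 criteria".

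**Death and relapse.** Appendix B puts "Death during treatment" in its Failure row. The Disease Progression row does not mention death. Section 9.a lists progressive disease and "The subject died during the study" as two separate ways to complete the study. Appendix B also has a row for relapse after CR or PR, whose blast criterion begins "Return to pretreatment bone marrow blast".

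**AML transformation.** Endpoint x in section 15.4 is "AML transformation according to World Health Organization (WHO) criteria". Inclusion criterion 4 in section 4.1 admits patients described as AML with 20-30% myeloblasts, and section 2.2 calls the same group oligoblastic AML. The WHO tables in Appendix C end at 19% marrow blasts for MDS and below 20% for CMML. The progression and relapse table of Appendix B has a transformation row that begins "Transformation to AML (30% or more blasts".

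**Population.** Section 15.4 opens with "This analysis will include all subjects who have received any protocol treatment, regardless of patient eligibility or duration of treatment".

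**LFS.** It is listed as an endpoint (synopsis, 3.2.11, 15.4) and is to be summarised by Kaplan-Meier. No event, time origin or at-risk set is given.

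**The concern.** Duration of response and the rate and time to AML transformation are named secondary objectives (sections 1.3.1 and 1.3.10). LFS is an objective in the synopsis. Section 15.4 plans estimates with 95% confidence intervals where feasible and expects the results to inform further study.

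As written, a response that ends in death without documented progression has no event date. That could happen fairly often. Section 2.2 takes about 8 months as the best estimate of median survival. Marrow is examined only every three cycles. End-of-treatment tests may be declined, and the off-treatment follow-up items in section 13 are vital status, death and AML transformation, not progression. Censoring those deaths would make responses look longer than they are.

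For AML transformation, some eligible patients are already beyond the threshold at entry. The reported rate would then move with the case mix at entry as well as with treatment.

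**Working it through.** The plan states no figure for these endpoints, so there is none to reproduce. The inputs s, q and p below are assumptions. The only related rate in the documents is the more than 30% progression to AML in untreated higher-risk MDS (section 2.1), used here as an anchor only.

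**1. Does death end a response?** Set side by side, the definition names only progression, Appendix B classes death as failure (and only during treatment), and section 9.a separates death from progression. Nothing makes death a form of progression, so there is no event.

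**2. Size if those deaths are censored.** Let the total hazard of a response ending be λ and the share due to death be s. The median with death as an event is ln2/λ. With deaths censored, the Kaplan-Meier median is ln2/((1-s)λ). The ratio is 1/(1-s):
- s = 10%: 1/0.90 = 1.11
- s = 25%: 1/0.75 = 1.33
- s = 50%: 1/0.50 = 2.0

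The direction is the same for any s above zero.

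**3. Does relapse end a response?** The relapse and progression rows share the granulocyte, platelet and transfusion criteria. They differ in two ways. Haemoglobin: a fall of 1.5 to <2 g/dL is relapse but not progression. Blasts: a patient in CR at 2% who returns to a pretreatment 4% has relapsed, but has not progressed because 4% is not above 5%. Appendix B does not say whether the blast increase is measured from the on-treatment low or from pretreatment. If from pretreatment, a return to that level is a zero increase and never progression, so the gap is wider. This is a minor clarification.

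**4. AML transformation.** The WHO boundary of 20% is inferred from inclusion criterion 4 and from where the Appendix C categories stop. Entrants at 20-30% have no new threshold to cross under it. Section 15.4 analyses all treated patients. Sections 15.1 and the synopsis describe an efficacy-evaluable set for all efficacy variables. Neither removes these entrants.

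Let p be the transformation rate in patients below 20% at baseline and q the share of 20-30% entrants. Kept in the denominator as never transforming, the rate is (1-q)p. Counted as events at baseline, it is q+(1-q)p.

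| q | p=30%: never | p=30%: baseline event | p=40%: never | p=40%: baseline event |
|---|---|---|---|---|
| 10% | 27% | 37% | 36% | 46% |
| 20% | 24% | 44% | 32% | 52% |
| 30% | 21% | 51% | 28% | 58% |

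**5. LFS.** With no definition, the problem carries over only if leukemia is read by the WHO criterion. If, further, these entrants were events at time zero, a constant hazard gives a median of ln(2(1-q))/ln2 times that of the <20% group: 0.85, 0.68 and 0.49 for q = 10%, 20% and 30%. That is one possible reading. If instead they had an event only at death, these ratios would not apply.

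**The case against.** **The documents never say that deaths will be censored.** Correct. The defect is that death has no event status. The overstatement follows only if deaths are then censored.

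**A reader might infer that 20-30% entrants will be counted as transformed at baseline, which would give the 37-51% figures.** The text does not support this as the natural reading. The endpoint is transformation, and section 13 collects its date only where applicable. A patient who enters with AML has none to record. Dilution by 1-q is the more realistic effect.

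**A reader might infer that LFS is WHO-defined and so has time-zero events.** It is not defined at all. The WHO reading is an assumption carried over from endpoint x.

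**A reader might set the 30% row aside because endpoint x cites WHO.** That goes too far. Section 14 sends progression to Appendix B, and the row sits in its progression and relapse table, so it can bear on duration of response and PFS. Under that row, entrants at 20-29% could still transform. The two thresholds need reconciling.

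**The all-treated sentence introduces the primary analysis, and the secondary list names no population.** Fair, but no alternative set in the documents excludes these entrants either.

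**The endpoints are exploratory and the inputs are assumed.** This stands, and it limits the weight of the point.

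**Conclusion.** The point holds as a correction to secondary endpoint definitions. Duration of response has no event for death without documented progression. If such deaths are censored, its median is overstated by 1/(1-s), assuming constant hazards and an s that the documents do not give. Under the WHO criterion, 20-30% entrants cannot newly transform, and leaving them in the denominator dilutes the AML rate by 1-q, with q unknown. Counting them as baseline events would inflate it, on a less natural reading. The WHO criterion and Appendix B's 30% row are unreconciled. LFS lacks a definition and shares the dilution or inflation problem only if leukemia is read by WHO.

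A reader might go further and doubt the trial's efficacy conclusion. The documents do not support that: the decision rule rests on the CR rate alone, and the synopsis calls these secondary analyses exploratory.

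**What to change.** 1. **Duration of response.** Define it as first response to the earliest of Appendix B relapse, progression or death from any cause, using the dates of loss of response and death that section 13 already collects. For HI responders, use the progression/relapse row for HI. Marrow CR has no relapse row, so use progression. State a censoring rule, for example last disease assessment for responders with no event by data cut-off. Say how the start of new treatment is handled, since censoring there may be informative.
2. **AML threshold.** State which threshold governs endpoint x and how the 30% row is used.
3. **Risk set.** If WHO governs, analyse AML transformation in patients with <20% blasts at baseline. Define LFS as time to AML transformation or death from any cause in the same patients. Report 20-30% entrants separately, with OS and, where marrow data exist, Appendix B progression.
4. **Optional.** If a time-based AML rate is reported, use cumulative incidence with death as a competing event.

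The cost is wording. Baseline marrow is required for all patients, and the needed dates are on the existing forms. The downsides are a shorter reported duration of response and an AML/LFS denominator smaller by the number of 20-30% entrants. Because end-of-treatment marrow may be declined, progression in that group will be incomplete.

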1.3.1. To determine the duration of response

1.3.2. To determine the proportion of patients with *TP53* mutant myeloid neoplasms alive at 8 months

1.3.3. To determine overall best response rates as measured by the international working group criteria (IWG 2006)

1.3.4. To determine if mutant TP53 variant allele frequency (VAF) or p53 protein expression predicts response to APR-246 with azacitidine

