We have recently analyzed our own experience on molecularly profiled patients at Moffitt Cancer Center and identified that the clonal burden, or variant allele frequency (VAF), had significant impact on clinical phenotype and more importantly further stratified prognosis over binary mutational analysis alone and/or clinical prognostic models¹⁹. Specifically, MDS patients with a *TP53* VAF > 40% had a median overall survival (OS) of 124 days versus an OS that was not reached in patients with VAF < 20% (hazard ratio (HR), 3.52; $P = 0.01$) with validation in an independent cohort (HR, 4.94, $P = 0.01$). Overall, *TP53* mutant MDS and AML patients have a median OS ranging from 5-9 months with 8 months representing the best estimate when restricting to MDS and oligoblastic AML (20-30% blasts)^{9,19-22}. Together, these data highlight the dismal outcomes of *TP53* mutant patients and the dire need for the development of novel therapeutic strategies, particularly in this patient population.

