Genoptix medical laboratory ([name]) will be the central laboratory for this study regarding molecular profiling. All patients will undergo baseline NGS for confirmation of *TP53* mutation, baseline *TP53* VAF, and identification of additional somatic mutations. These analyses will not impact enrollment into the clinical trial. Importantly, there will be serial evaluation following cycle 3 and cycle 6 where NGS will be repeated to evaluate for clonal reduction of *TP53* VAF as well as changes in the underlying mutational architecture of these patients. These analyses will be utilized for secondary endpoints #4-7. **For correlative genomic studies that will be performed at Genoptix medical laboratory, 2-3 mL of peripheral blood will be obtained in a standard Vacutainer tube with EDTA (purple top) as anticoagulant. If *TP53* mutation is only present on BM analysis at screening, serial NGS myeloid panel**

can be performed on bone marrow MNC. A FedEx shipping label will be included in the shipper box with a research specific requisition. Recurrent gene mutations of *ASXL1*, *BCOR*, *BRAF*, *CALR*, *CBL*, *CEBPA*, *CSF3R*, *DNMT3A*, *ETV6*, *EZH2*, *GATA2*, *GNAS*, *IDH1*, *IDH2*, *JAK2*, *KIT*, *KRAS*, *MPL*, *NF1*, *NPM1*, *NRAS*, *PDGFRA*, *PDGFRB*, *PHF6*, *PTPN11*, *RAD21*, *RUNX1*, *SETBP1*, *SF3B1*, *SMC1A*, *SMC3*, *SRSF2*, *STAG2*, *STAT3*, *STAT5b*, *TET2*, *TP53*, *U2AF1*, *WT1*, and *ZRSR2* will be evaluated at each NGS analysis. DNA and RNA will be isolated from BM-MNC by the Ficoll method following cycle 3 and cycle 6 and stored in the laboratory of [name]. In patients who become negative for *TP53* mutation by NGS (VAF sensitivity for this assay is 1% in patients with previously identified variants), we will perform PCR-based barcoding or digital droplet PCR to identify rare variants in an effort to determine the depth of remission induced by treatment with APR-246 and azacitidine.

2. Immunohistochemistry for p53 expression

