BM core biopsies will be centrally evaluated at Moffitt Cancer center by [name] to evaluate for p53 protein expression as a biomarker of response, correlation with *TP53* VAF, and serially over the course of treatment (secondary endpoints # 4-5). Three sections from each core biopsy will be obtained at baseline and following cycle 3 and 6 of therapy. To evaluate for p53 protein expression, p53 IHC will be performed using a standard protocol (p53 antibody, clone Bp53-11, Ventana Medical Systems, Tucson, AZ, USA). Nuclear p53 expression will be assessed quantitatively by percent p53 positivity and semi-quantitatively with an IHC score of stain intensity (0, 1+, 2+, and 3+) multiplied by percent positive hematopoietic cells.

Shipping

Bone marrow core biopsies will be shipped to the below address.

H. Lee Moffitt Cancer Center

[name]

[name]

[name]

[contact]

3. *In vivo* evaluation of APR-246

As the primary mechanism of action of APR-246 is restoration of wild-type function of p53, we will utilize the lead in phase of APR-246 monotherapy to assess the activation of downstream targets of p53. An additional 20ml of bone marrow aspirate will be obtained in purple EDTA tubes at the pre-study bone marrow (prior to Cycle #1) and on day -10 following four days of APR-246 as well as at disease assessments (following cycle 3 and cycle 6; see study calendar). Utilizing the bone marrow aspirates, the mononuclear

cells will be collected with isolation of DNA and RNA as previously described and stored in the laboratory of [name]. Evaluation of p53-mediated signal transduction will be analyzed using Qiagen human p53 Signaling Pathway RT² Profiler PCR Array (secondary endpoint #8). As production of ROS leading to DNA damage is an additional mechanism of action of APR-246, we will evaluate for ROS production before and after APR-246 monotherapy via flow cytometry (CellROX® Deep Red Reagent, Life Technologies; secondary endpoint #9).

i. Shipping

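### Response is compared by marker only across two-group splits; the p53 split has neither a named measure nor a cut-point, and no analysis relates response to either marker on its graded scale

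*Combined protocol and SAP*

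**What the plan says.** Section 1.3.4 sets the objective: "To determine if mutant TP53 variant allele frequency (VAF) or p53 protein expression predicts response to APR-246 with azacitidine". The matching analysis is secondary endpoint iv in Section 15.4, the "Proportion of subjects who obtain a response as defined by IWG 2006 criteria with a baseline" VAF at or above 20% compared with below 20%, "or high versus low nuclear p53 protein expression". The synopsis carries the same endpoint. Section 3.2.4 lists the VAF comparison but omits p53.

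Both markers are recorded on graded scales. Section 16, item 1 states "All patients will undergo baseline NGS for confirmation of" the mutation, and the same baseline assay gives VAF. Section 16, item 2 describes p53 in two ways: "Nuclear p53 expression will be assessed quantitatively by percent p53 positivity and semi-quantitatively with an IHC score of stain intensity", the score being intensity graded 0 to 3+ times percent positive cells. No section says which of the two defines high and low, or where the boundary lies.

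Endpoint v correlates VAF with p53 expression, so graded values may be used there, but not against response. Section 15.4 treats these endpoints as exploratory, with estimates and 95% intervals where feasible. It names no test for endpoint iv.

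**The concern.** There are two separate problems.

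- **An open choice for p53.** With two measures and no cut, the grouping can be settled after response is known, in an open-label single-arm trial. A cut chosen because it separates responders from non-responders exaggerates the apparent association. Section 15.4 expects these data to inform later work, so a data-chosen biomarker boundary could be carried forward.
- **Lost information for both markers.** The objective asks about prediction, but the plan only compares proportions between two groups. If response changes steadily with the marker, a split throws away part of what was measured, and an uneven split throws away more.

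The VAF cut does not share the first problem, because 20% is written into the plan.

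**Working it through.** **Inputs from the plan.** n = 24 + 21 = 45 at the MTD (Section 15.1). The plan gives no figure for endpoint iv. Its only operating characteristics belong to the Simon design, and they reproduce: the probability of 5 or fewer CRs in 24 at a 20% rate is 0.656 (stated 0.66), power at 40% is 0.9001 (stated 0.90), and exact type I error is 0.0483 (stated limit 0.05).

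**Inputs that are assumed.** The documents do not give the marker distributions, the share of patients below 20% VAF, the response rate for this endpoint, or the effect size. Ranges are shown instead.

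**Step 1: information kept by a split.** Let q be the share in the smaller group. Relative to the continuous marker with a linear effect, the efficiency is φ(z_q)² / [q(1−q)] for a normal marker and 3q(1−q) for a uniform one. At q = 0.5 these give 0.3989² / 0.25 = 0.637 and 3 × 0.25 = 0.75.

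| Split | Normal | Effective patients of 45 (normal) | Uniform |
|---|---|---|---|
| 50/50 | 64% | 28.6 | 75% |
| 30/70 | 58% | 25.9 | 63% |
| 20/80 | 49% | 22.0 | 48% |
| 10/90 | 34% | 15.4 | 27% |

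The best-case loss is therefore 25% to 36%. The loss passes half at q of about 0.21 in both cases (normal: 50.1% kept at 0.21; uniform: 3q(1−q) = 0.5 gives q = 0.211), which is about 9 of 45 patients.

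**Step 2: power when the effect is linear on the logit scale.** Normal marker, n = 45, two-sided 5%, 3,000 simulated trials per setting. The continuous analysis is a logistic likelihood-ratio test and the split is an uncorrected chi-square test. Overall response is 40%.

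| Odds ratio per SD | Continuous | 50/50 | 20/80 | 10/90 |
|---|---|---|---|---|
| 2.0 | 57% | 39% | 25% | 11% |
| 2.5 | 78% | 58% | 38% | 15% |
| 3.0 | 89% | 70% | 50% | 20% |

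At 60% response and an odds ratio of 2.5 the figures are 77% continuous, 57% for 50/50, 50% for 20/80 and 35% for 10/90.

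**Step 3: VAF-like distributions cut at 20%.** Beta(2, 2.5), Beta(1.2, 1.8) and Beta(1.5, 3) put about 14%, 26% and 30% of patients below 20% VAF, or about 6 to 14 of 45. Response is about 50%.

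- Linear, slope 1.0 per SD (odds ratio e^1.0 = 2.7): split 28% to 50% with Fisher's test, 37% to 57% with chi-square; continuous about 85% to 88%.
- Linear, slope 0.7 (odds ratio 2.0): Fisher 16% to 29%; continuous about 60%.
- Linear, slope 0.4 (odds ratio 1.5): continuous only about 25% to 28%.
- Step at 20% (log-odds −1.5 below, +0.3 above): Fisher 35% to 66%; continuous 21% to 45%. The ranking reverses.

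Under the null, Fisher's test rejects in 2% to 4% of trials and the likelihood-ratio test in about 5% to 7%, so part of the linear-case gap is a difference in test size.

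**Step 4: cost of choosing the p53 cut late.** Null marker, n = 45, response 40%, nominal 5%, 4,000 simulated trials. The share of trials with an apparently significant difference is:

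- one fixed median cut: 4.8%
- best of three quartile cuts: 12.7%
- best of all cuts between the 20th and 80th percentiles: 30.6%
- best of seven decile cuts on either of two measures correlated at 0.8: 32.8%

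This step needs no assumption about VAF.

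**The case against.** The strongest defence is that the endpoint is exploratory. No test, alpha or power is claimed for it, and the stage 1 and final decisions use CR alone. This stands and limits the severity. It does not close the p53 gap, because a late choice of cut also biases an estimated difference and its interval.

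It can also be said that the power comparison favours the model that generated the data. That is right: step 3 shows the split ahead when the true effect is a step at 20%, and the documents do not say which shape holds. Even under linearity, a modest association would probably be missed either way. These are reasons to keep the VAF table and add the continuous analysis beside it.

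A reader might go further and infer three things that the documents do not support:

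- **That the splits discard most of the information.** This holds only if about one fifth or fewer of patients fall on one side. That share is not given for VAF, and it cannot be worked out for a p53 split with no cut.
- **That few patients will be below 20% VAF.** This is an assumption about the distribution.
- **That Section 2.2 shows a gradient in response above 20%.** Its contrast is in survival: patients above 40% VAF "had a median overall survival (OS) of 124 days", while the median was not reached below 20%. The same section reports that TP53 mutation shortened survival under hypomethylating agents without affecting response rates.

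**Conclusion.** The point holds in two parts. The p53 comparison is undefined in both measure and cut. That is a plain gap in the text, and an unrestricted search could raise a nominal 5% false-positive rate to about 31% to 33%. Separately, no planned analysis relates response to either marker on its graded scale, although the objective asks whether they predict it. The information lost is about one quarter to one third at best for a normal or uniform marker with a linear effect, and more with unequal groups.

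The power figures rest on assumed distributions, assumed effects and rough linearity on the logit scale; they do not show that the continuous analysis must do better. The VAF cut is pre-specified and raises no post hoc concern. Severity is low to moderate: the endpoint is exploratory and the CR decision is untouched, but the correction is nearly free.

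**What to change.** - Add to endpoint iv a logistic regression of IWG response on continuous baseline VAF and, separately, on one named continuous p53 measure (percent positivity or the intensity-times-percent score). Report odds ratios with 95% confidence intervals.
- Keep the pre-specified 20% VAF table beside the regression.
- Either drop the high/low p53 comparison, or state its measure and numeric cut before response data are reviewed.
- Align Section 3.2.4 with the synopsis and Section 15.4 on whether p53 is part of this endpoint.

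The cost is SAP wording only. The plan already collects every value needed, and no sample size, visit or assay changes.
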